9.1.1 Primary endpoint

The primary endpoint is:

- Occurrence, duration, treatment, seriousness, and outcome of AEs², SAEs, ARs, and FVIII inhibitor from study start to end of study

9.1.2 Secondary endpoints

The secondary endpoints are:

- Number of ARs that are defined within the system organ classes nervous system and psychiatric disorders from study start to end of the study
- Number of ARs related to hepatic or renal function from study start to the end of the study
- Change in kidney and liver function parameters from study start to the end of the study
- Change in PEG-plasma levels from study start to the end of the study
- Number of patients with abnormal findings as assessed by neurological examination across all age groups from study start to the end of the study

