9.3 Variables

The physician collects historical study-relevant data (demographic and clinical characteristics) from medical records if available (or by interviewing the patient at the initial [baseline] visit) and treatment-related data during visits (see section 9.2.5). In this non-interventional study, the visits are not scheduled by the study team (i.e. visits occur at the physicians' discretion and independent of the

⁶ Events up to 30 days after the last dose of damoctocog alfa pegol within the study period.

⁷ Including duration, treatment, seriousness and outcome.

⁸ Sodium, potassium, albumin, creatinine, bilirubin, aspartate aminotransferase (AST), alanine aminotransferase (ALT), gamma-glutamyl transferase (GGT), alkaline phosphatase, C-reactive protein (CRP), urea, estimated glomerular filtration rate (eGFR).

⁹ Urine albumin/creatinine ratio, spot urine dipstick test.

¹⁰ Including (for all ages) level of consciousness, cranial nerves, body tone, strength (of the four extremities), reflexes, sensory aspects, gait and coordination and fine motor function. In the case of children, evaluation of appearance, language, social interaction. In the case of adults, mental state.

patients' participation in the study. It is assumed that at most Hemophilia treatment centers; patient visit frequency is at least 1-2 times per year). The physician documents the study-relevant data for each patient in the eCRF/EDC system. The pCRF (paper version of the eCRF) is kept as a stand-alone document (see [Table 3](#)) and is available upon request.

This is a non-interventional study and the clinical decisions of the physicians must not be affected by study participation. As such, data on many of the secondary endpoints (e.g. PEG-plasma, eGFR, ALT) may not be available for all patients. Nevertheless, if they were collected in local routine clinical practice at the investigator's discretion, all results will be documented in the eCRF/EDC system. In the case that an investigator wants to determine the PEG levels in plasma, e.g. in case of any AE which could be related to PEG accumulation, one or more laboratories will be appointed and kits will be provided to the sites for sampling as per the investigator's discretion. Bayer Consumer Care AG will offer support for the procedure if requested.

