9.7.3 Analysis of primary variable(s)

The analysis described in this section will be performed based on adverse events (AEs) on the SAF.

An overview table displaying all AEs will be presented. This overview table will provide a summary on patient-level:

- Any event (AE of special interest, AE, SAE, and AR).

- Maximum intensity of events.
- Events with the outcome of death.
- Events leading to a change of treatment regimen of study treatment.
- Events leading to discontinuation of study treatment.
- Events related to inhibitor development.

AEs will be coded using the latest version of MedDRA. A summary of AEs will be presented by the primary System Organ Class (SOC) and Preferred Term (PT). AEs will primarily be classified by MedDRA PT. Aggregated incidences at the SOC level will also be presented.

Each of the AEs of special interest will be described separately. Event rates and 95% CIs will be reported as both incidence risks and exposure-adjusted incidence rates per patient.

Additionally, a detailed listing will be provided for AEs related to the development of an inhibitor or positive inhibitor measurements, including information on the history of inhibitors.

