11.1 Definitions

An Adverse Event (AE) is any untoward medical occurrence in a patient administered a medicinal product and which does not necessarily have a causal relationship with this treatment. An AE can, therefore, be any unfavorable and unintended sign (e.g., an abnormal laboratory finding), symptom, or disease temporally associated with the use of a medicinal product, whether or not considered related to this medicinal product [35].

The term also covers laboratory findings or results of other diagnostic procedures that are considered to be clinically relevant (e.g., that require unscheduled diagnostic procedures or treatments or result in withdrawal from the study).

- The AE may be:
- A new illness.
- Worsening of a sign or symptom of the condition under treatment or of a concomitant illness.
- An effect of the study treatment.
- An effect of a concomitant medication or treatment.
- Off label use¹¹, occupational exposure, lack of drug effect, medication error, overdose, drug abuse, drug misuse or drug dependency itself, as well as any resulting event.
- An effect related to pre-existing condition improved (unexpected therapeutic benefits are observed).
- Product exposure via mother/father (exposure during conception, pregnancy, childbirth, and breastfeeding).

As mentioned above no causal relationship with a product is implied by the use of the term “adverse event”.

An Adverse Reaction (AR) is defined as a response to a medicinal product which is noxious and unintended. An AR is any AE judged as having a reasonable suspected causal relationship to damoctocog alfa pegol.

Causal relationship: The assessment of the causal relationship between an AE and the administration of treatment is a clinical decision based on all available information at the time of the completion of the eCRF. The assessment is based on the question of whether there was a “reasonable causal relationship” to the study treatment in question. Possible answers are “yes” or “no”.

An assessment of "no" would include:

- The existence of a clear alternative explanation (e.g., mechanical bleeding at the surgical site).

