11.2 Collection

It should be documented in the eCRF whether the patient is participating in a registry or other program where reporting of AEs to a third party may occur in addition to the reporting requirements for this study.

Starting with the first administration of damoctocog alfa pegol after enrollment into the study, all non-serious AEs must be documented on the AE Report Form or in the eCRF/EDC system and forwarded to the Marketing Authorization Holder (MAH) within 7 calendar days (for EU countries or if required by local regulations of participating country) or 60 days (for countries outside the EU) of awareness. All SAEs must be documented and forwarded immediately (within 1 business day of awareness). For each AE, the physician must assess and document the seriousness, duration, relationship to the product, action taken and outcome of the event.

If a pregnancy in the female partner of a male patient or in a female patient occurs during the study, although it is not an SAE itself, it should be documented and forwarded to the MAH within the same time limits as an SAE. The result of pregnancy will be followed-up according to applicable Bayer

standard operating procedures. Any data on abnormal findings concerning either the mother or the baby will be collected as AEs.

The documentation of any AE/SAE ends at the latest 30 days after the completion of the observation period of the patient: i.e., any AE/SAE - regardless of the relationship and the seriousness - occurring up to 30 days after the last dose of damoctocog alfa pegol within the patient's observation period has to be documented and forwarded to the MAH within the given timelines.

As long as the patient has not received any damoctocog alfa pegol within the frame of the study AEs/SAEs do not need to be documented as such in this non-interventional study. However, they are part of the patient's medical history.

For any serious product-related AE occurring after study end, the standard procedures that are in place for spontaneous reporting have to be followed.

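### Two of the five secondary endpoints count only events the physician attributes to the drug, which leaves hepatic events without a grouped count regardless of causality

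*Protocol*

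**What the plan says.** Protocol section 9.1.2 lists five secondary endpoints. Two count ARs: "Number of ARs that are defined within the system organ classes nervous system and psychiatric disorders from study start to end of the study" and "Number of ARs related to hepatic or renal function from study start to the end of the study". Section 11.1 defines the term: "An AR is any AE judged as having a reasonable suspected causal relationship to damoctocog alfa pegol". The judgement is a yes or no. Section 11.2 assigns it to the physician, who for each AE has this duty: "the physician must assess and document the seriousness, duration, relationship to the product, action taken and outcome of the event".

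Two further secondary endpoints cover the same organs with no causality condition: "Change in kidney and liver function parameters from study start to the end of the study" and "Number of patients with abnormal findings as assessed by neurological examination across all age groups from study start to the end of the study". The fifth is the change in PEG plasma levels. On completeness, section 9.3 warns that "data on many of the secondary endpoints (e.g. PEG-plasma, eGFR, ALT) may not be available for all patients".

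The primary endpoint (section 9.1.1) covers AEs and SAEs as well as ARs. Section 9.7.3 tabulates all AEs by system organ class (SOC) and preferred term (PT), and adds: "Aggregated incidences at the SOC level will also be presented". It also describes each AE of special interest separately, with incidence risks, exposure-adjusted rates and 95% CIs. Section 11.3 lists five such events: hypersensitivity, inhibitor development, loss of drug effect, renal impairment and neurocognitive disorders.

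**The concern.** The secondary objective (section 8.2) is to monitor clinical effects of long-term exposure, including kidney, liver and neurological function. It is not limited to effects that a physician already suspects. The two AR counts are limited in that way. A slow or non-specific effect is one that a physician could reasonably put down to something else, and section 11.1 directs a negative answer where a clear alternative explanation exists.

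Nothing in the design corrects a mistaken attribution. The checklist in Annex 2 marks a comparator as not applicable (item 5.6) and analytic control of outcome misclassification as absent (item 10.6). A low AR count could therefore reflect what physicians expect of the drug as much as what the drug does.

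Section 9.9 sharpens the point. It accepts that laboratory and neurological data may be incomplete, and relies on any clinically relevant change in organ function being recorded as an AE. That safeguard yields an AE, yet the organ-specific event endpoint counts only ARs. The event meant to make up for a missing test is left out of that endpoint unless it is judged related.

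**Working it through.** **Step 1: what each endpoint counts, by organ area.**

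| Area | AR-only endpoint (9.1.2) | Planned summaries with no causality condition |
|---|---|---|
| Nervous system, psychiatric | Yes, defined by SOC | All-AE incidence for the same SOCs (9.7.3); neurocognitive disorders as AE of special interest, with rates and CIs (9.7.3, 11.3); abnormal neurological findings (9.1.2) |
| Renal | Yes, defined by function | Renal impairment as AE of special interest, with rates and CIs; change in kidney parameters (9.1.2); out-of-range counts (9.7.4) |
| Hepatic | Yes, defined by function | Change in liver parameters (9.1.2); out-of-range counts (9.7.4); separate SOC and PT rows (9.7.3) |

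The hepatic row alone has no grouped event summary regardless of causality. The endpoint there is defined by function, not by SOC. Section 11.1 counts clinically relevant laboratory findings as AEs, and section 9.7.3 promises rows by SOC and PT only. The protocol does not say that those rows would bring all hepatic-function events together.

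**Step 2: the plan's own figure.** Section 9.5 gives a 64% chance of at least one event among 50 patients at a 2% risk. Check: 1 − 0.98^50 = 0.636. It reproduces, and it does not depend on the choice between AR and AE.

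**Step 3: illustration of the loss.** Let s be the fraction of events that the physician attributes to the drug. The documents give no value, so s is an assumption. An AR-only count then sees a risk of 0.02 × s, and the chance of at least one counted event in 50 patients is 1 − (1 − 0.02s)^50:

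| s | Chance of at least one counted event |
|---|---|
| 1 (all AEs) | 63.6% |
| 0.75 | 53.0% |
| 0.50 | 39.5% |
| 0.25 | 22.2% |
| 0.10 | 9.5% |

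The 2% is the protocol's general example, not a hepatic risk.

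Alternatively, fix the number k of true drug-caused events and assume that each is attributed independently with probability q. The expected AR count is k × q and the chance of a zero count is (1 − q)^k. Over an assumed range of 20% to 50%:

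- k = 3: 0.8^3 = 51% at q = 0.20; 0.5^3 = 12.5% at q = 0.50.
- k = 6: 0.8^6 = 26% at q = 0.20; 0.5^6 = 1.6% at q = 0.50. The expected count is 6 × 0.20 = 1.2 to 6 × 0.50 = 3.

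The all-AE primary endpoint is unaffected at any s or q.

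**The case against.** The strongest reply is that these are two supplementary counts in a descriptive study. A reader might infer from their wording that unattributed events disappear, or that the study presupposes the answer to its own causal question. The documents do not support that. Section 11.2 requires AEs to be documented whatever their relationship to the drug, section 9.1.1 counts them in the primary endpoint, and section 9.7.3 tabulates them. The filter acts on two endpoint tabulations, not on data capture for these organ areas.

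A reader might also infer that hepatic effects have no summary free of attribution. That too goes too far: section 9.3.2 lists AST, ALT, GGT, bilirubin and alkaline phosphatase, and section 9.7.4 reports change from baseline and the number of patients out of range. These data depend on routine practice, but incomplete is not absent.

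Other parts of the reply also stand. For nervous system and psychiatric events, the all-AE counterpart is largely planned already at SOC level. Renal impairment is protected by its special-interest status. The threshold for an AR is a reasonable suspicion, which is permissive, so low attribution fractions cannot be taken for granted.

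It can further be said that a PT list and table layout belong in the SAP, to which section 9.7.1 assigns table content. That is fair for the list itself. It does not cover the endpoint definition, which section 9.1.2 fixes as ARs.

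**Conclusion.** The point holds in a limited form. Two of the five secondary endpoints are open to attribution bias, because the physician's judgement decides what enters the count and there is no comparator to check it against. The practical gap is chiefly hepatic: these events are not of special interest, and the protocol plans no grouped AE count for them regardless of causality. The renal and neurocognitive areas are largely covered elsewhere, and other nervous system and psychiatric events have all-AE figures at SOC level.

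The size cannot be estimated from the documents. The figures above, including the 51% chance of a zero count after three true events, rest on assumed attribution fractions and independent judgements, and show direction only. The change is worth making because it is specific and uses data already collected. It does not call the primary analysis into question.

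**What to change.** In section 9.1.2, reword the hepatic and renal bullet to the number of AEs, and the number of patients with AEs, concerning hepatic or renal function regardless of causality, including AEs that are laboratory findings. Report exposure-adjusted rates with 95% CIs and keep the AR count as a sub-row. The terms that make up the group can be listed in the SAP.

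For the nervous system and psychiatric bullet, show the all-AE SOC figures already planned in section 9.7.3 beside the AR count.

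The cost is a change of endpoint wording and a small addition to the tables, with no new data collection. Unrelated background events will enter the hepatic and renal count; the AR sub-row keeps the physician's attribution visible.

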7.2 Rationale

Damoctocog alfa pegol is a B-domain–deleted recombinant factor VIII (BDD-rFVIII) that is site-specifically conjugated with a 60-kDa branched polyethylene glycol (PEG) molecule at a cysteine that has been introduced into the A3 domain (K1804C) resulting in 1 PEG per BDD-rFVIII protein [6]. This addition of PEG prolongs the duration of FVIII in circulation while retaining its full coagulant activity [7],[8]. Damoctocog alfa pegol (Jivi) is approved for prophylaxis and treatment of bleeds in previously treated patients (PTPs) with hemophilia A aged ≥ 12 years, with a two times per week, every five days or every seven days dose that allows for the treatment regimen to be tailored to individual patient needs. An enhanced pharmacokinetic (PK) profile enables a potentially decreased dosing frequency compared with unmodified rFVIII. Efficacy and safety of prophylaxis dosing with damoctocog alfa pegol were demonstrated in 2 phase II/III clinical studies in adult, adolescent, and pediatric (<12 years of age) PTPs with severe hemophilia A [9],[10].

The aim of the proposed study is to characterize in a real-world setting the long-term safety of damoctocog alfa pegol drug usage. The study design will allow for fulfilling the post-approval commitment to the European Medicines Agency (EMA). In accordance with the EMA requirements regarding sample size and observation time, the study aims to observe 50 patients for at least 4 years

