each. Detailed information will be collected on reported adverse events (AEs) of special interest including hypersensitivity reactions, loss of drug effect, renal impairment, neurocognitive disorders, inhibitor development, and serious adverse events (SAEs). These parameters will assess if there are any potential safety risks of long-term PEG exposure. The AEs of hypersensitivity and loss of drug effect are related to the class of FVIII replacement therapy. Since damoctocog alfa pegol is a PEGylated product, immunogenicity related to the PEG component can occur. Although the 60 kDa PEG that is part of the damoctocog alfa pegol molecule is larger than the 20-40 kDa PEG moieties on other FVIII replacement products, the low content of PEG associated with the site-specific PEGylation of damoctocog alfa pegol results in a lower PEG load (PEG amount per treatment or per week) and consequently in plasma and tissues relative to some other PEGylated products. The preclinical toxicology studies demonstrated an absence of any pathological effects. The low peak plasma level of approximately 0.1 mg/L at steady state in humans is consistent with these pre-clinical data. No increase in PEG plasma levels has been observed in the clinical studies including the extension studies in more than 100 patients with a total treatment period of at least 3 years up to 6 years¹.

The results of this observational study aim to add to the knowledge of the safety profile of real-world prophylaxis with damoctocog alfa pegol.

Prior to finalization of the present HA-SAFE protocol v1.0, protocol version 0.5 was endorsed by the PRAC on 28 November 2019 (as confirmed in the outcome letter dated 05 December 2019).

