7.3 Background

Prophylaxis with FVIII reduces bleeds and improves joint outcomes in patients with severe hemophilia A [11],[12],[13],[14], and it is, therefore the standard of care in most developed countries [1],[15]. However, adherence to prophylaxis is poor in some patients [16]. This may be due to the high time burden and inconvenience of a typical prophylaxis regimen, which requires intravenous infusion at least 2 or 3 times per week [17],[18],[19]. Thus, prolonged-half-life FVIII products that allow for less frequent, individualized dosing may increase adherence and ultimately lead to improved clinical outcomes, including prevention of joint disease [20],[21],[22].

In a phase I study of 14 patients, damoctocog alfa pegol had a half-life of ~19 hours versus ~13 hours for sucrose-formulated rFVIII [7]. In the phase II/III PROTECT VIII study [10] safety was comparable to that observed with other FVIII products [23],[24],[25],[26],[27]. Patients and physicians can choose from 3 effective prophylaxis regimens with damoctocog alfa pegol based on individual patient bleeding profile and lifestyle. However, outside of the clinical study, there are currently little real-world safety data on the use of the product.

8. Research questions and objectives

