9.1 Study design

This is a multinational, open-label, prospective, non-interventional, multicenter, cohort study of PTPs with hemophilia A receiving damoctocog alfa pegol as prophylaxis treatment. The study is planned to be conducted in multiple countries in Europe.

At study start, retrospective data will be collected on the patients' baseline characteristics (including genotyping [where available], medical condition and hemophilia treatment history). Also at study start and then at each physician visit during the follow-up phase, data will be recorded on regimens used, AEs of special interest including hypersensitivity reactions, loss of drug effect, renal impairment, neurocognitive disorders, inhibitor development, other AEs, SAEs and drug-related ARs in standard clinical practice. If collected in routine clinical practice at the physician's discretion, parameters relating to kidney and liver function (e.g. creatinine, estimated glomerular filtration rate (eGFR), alanine transaminase (ALT), aspartate aminotransferase (AST), bilirubin), PEG-plasma level and abnormal findings from neurological assessments will be captured in the eCRF/EDC system. Adverse reactions (ARs) relating to the system organ classes of the nervous system and psychiatric disorders will be recorded.

Patients/legal representatives and physicians can choose from different prophylaxis regimens with damoctocog alfa pegol following approved local labels or any other regimen prescribed by the physician as part of normal clinical practice. Patients/legal representatives and physicians can choose to change the dosing regimen based on the patient's response to treatment at any time. A reason for the dose and/or frequency change should be documented.

The planned observation period for each of at least 50 patients will be a minimum of 48 months for the collection of long-term safety data and the prospective monitoring of clinical effects of long-term exposure of prophylaxis with damoctocog alfa pegol in PTPs with hemophilia A.

Due to the observational nature of the study, follow-up visits cannot be scheduled specifically for study purposes and it is unknown when a patient will come for the next visit. Thus, data collection will occur continuously throughout the patient's observational period (i.e., each visit or assessment

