The final data collection (end of observation) should be after 50 patients have been followed-up for a minimum of 4 years.

Final collection of safety data (e.g. AEs) will occur up to 30 days after the last dose of damoctocog alfa pegol within the study period.

Lost to follow-up

A patient is considered ‘lost to follow-up’ if no further information can be expected from the patient at a given point in time.

If no information had been obtained from a patient within 12 months from the last data collection time point, site personnel are requested to apply due diligence (within the applicable legal limits) to contact patients and ascertain the reason for an absence of information. In case no information can be obtained, the site should confirm that the patient is lost to follow-up and document the end of observation.

Table 2: Overview of information collected during the initial visit and at subsequent follow-up visits

	Enrollment / Initial visit	Follow-up visit (including end of observation)
Eligibility assessment ³	X	
Date of visit	X	X
Date of informed consent	X	
Demographic data ⁴ (e.g. date of birth or age; ethnicity, race)	X	
Hemophilia disease history, mutation genotype	X	
Hemophilia treatment history (including Damoctocog alfa pegol history, if any)	X	
Medical history and concomitant diseases	X	
Physical examination (e.g. weight, height, vital signs)] ⁵	X	X
Prior and concomitant medications	X	X

³ Including confirmation of eligibility criteria or documentation of reason for non-enrolment, where applicable (see 9.2.4)

⁴ The availability of demographic variables is likely to vary per country according to legal and ethical regulations. Race will only be collected where legally permitted

⁵ If available (i.e. if conducted during routine clinical examination).

	Enrollment / Initial visit	Follow-up visit (including end of observation)
Currently prescribed damoctocog alfa pegol regimen	x	x
Damoctocog alfa pegol dose/regimen changes, treatment switches		x (continuous collection)
Damoctocog alfa pegol pharmacokinetic analysis ⁵	x	x
Adverse events, Serious adverse events and Adverse reactions (includes systematically collected AEs and AEs of special interest) ^{6,7}	x (continuous collection)	
FVIII inhibitor ⁵	x	x
Biochemistry ^{5,8}	x	x
Urinalysis ^{5,9}	x	x
PEG-plasma ^{5,6}	x	x
Neurological assessment ^{5,10}	x	x
Number of bleeding episodes	x	x
Reason(s) for end of observation		x (at occurrence)

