9.7.4 Analysis of secondary variables

Laboratory parameters will be analyzed descriptively. Results will be displayed by summary statistics and as change from baseline.

A descriptive analysis will be performed for the number of patients with laboratory parameters outside of the normal ranges.

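### PEG plasma change is an endpoint, but the listed variables do not show when a sample was taken relative to the last infusion

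*Protocol*

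**What the plan says.** The protocol's secondary endpoints (9.1.2) include "Change in PEG-plasma levels from study start to the end of the study". PEG is listed among the laboratory parameters in 9.3.2, and for these section 9.7.4 states: "Results will be displayed by summary statistics and as change from baseline".

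Sampling is not tied to the infusion cycle. Section 9.1 says that "follow-up visits cannot be scheduled specifically for study purposes". Section 9.3 leaves PEG sampling to the investigator, with a suspicious adverse event as the example of a trigger, and says that "one or more laboratories will be appointed and kits will be provided to the sites for sampling".

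The only timing item that 9.3.2 lists for laboratory tests, PEG included, is the date of the test. Table 2 (9.2.5) has a row for "Currently prescribed damoctocog alfa pegol regimen", a row for dose and regimen changes collected continuously, and a pharmacokinetic row completed if available. It has no row for the last infusion before a sample. Footnote 6, which reaches 30 days after the last dose, is attached to the PEG row. The patient diary is described only as a source of adverse events.

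The background sections treat the level as depending on time after dose. Section 7.2 refers to "The low peak plasma level of approximately 0.1 mg/L at steady state in humans". Section 7.3 reports that "damoctocog alfa pegol had a half-life of ~19 hours versus ~13 hours for sucrose-formulated rFVIII". Section 7.2 describes the product as approved "with a two times per week, every five days or every seven days dose", and 9.1 allows other regimens and changes between them.

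**The concern.** The PEG is attached to the infused molecule, so plasma PEG should rise with each infusion and fall until the next. If one sample is taken shortly before an infusion and a later one shortly after, the level appears to rise although nothing has accumulated. In the reverse order, a real rise can be masked. A sample taken up to 30 days after the last dose would add wash-out to the same change.

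Possible PEG accumulation is named in the primary objective, and plasma PEG is the study's direct measurement of it. With about 50 to 60 patients and discretionary testing, individual changes will be read one by one, and these are the values that timing disturbs. This is a matter of data capture: an analysis plan can only use an infusion time that was collected.

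**Working it through.** The protocol gives a peak but no trough and no expected within-interval change, so there is no stated figure to reproduce.

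**Inputs from the protocol.** Drug half-life about 19 h (7.3). Peak about 0.1 mg/L (7.2). Dosing intervals τ of 84 h (twice weekly, taken as half a week), 120 h and 168 h (7.2).

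**Assumption.** No half-life T for plasma PEG is given. I use 19 h as one case and assumed values of 72 h, 168 h (7 days) and 720 h (30 days) as the range.

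**Step 1: fall from peak to next dose.** With mono-exponential decline, the ratio is 2^(τ/T). For example, 2^(84/19) = 21.4 and 2^(168/72) = 5.0.

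| T | τ = 84 h | τ = 120 h | τ = 168 h |
|---|---|---|---|
| 19 h (drug) | 21-fold | 80-fold | 459-fold |
| 72 h (assumed) | 2.2-fold | 3.2-fold | 5.0-fold |
| 168 h (assumed) | 1.4-fold | 1.6-fold | 2.0-fold |
| 720 h (assumed) | 1.1-fold | 1.1-fold | 1.2-fold |

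From a peak of 0.1 mg/L, T = 19 h leaves 0.0047, 0.0013 or 0.0002 mg/L before the next dose. T = 720 h leaves 0.092, 0.089 or 0.085 mg/L.

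**Step 2: two samples at random times, no true change.** The table shows the extreme pair. For two sampling times spread evenly over the interval, the chance that the second value is at least double the first is 0.5 × (1 − T/τ)² when T < τ, and zero otherwise.

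- T = 19 h: 0.5 × (1 − 19/84)² = 30%; likewise 35% at 120 h and 39% at 168 h. A simulation of 400,000 pairs per case agreed.
- T = 72 h: 0.5 × (1 − 72/84)² = 1%; 0.5 × (1 − 72/120)² = 8%; 0.5 × (1 − 72/168)² = 16%.
- T = 168 h or more: 0%.

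By symmetry, the same shares are the chance that a true doubling shows as no rise.

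**Step 3: sample 30 days after the last dose.** The fraction left is 2^(−720/T): practically nothing at 19 h, 0.1% at 72 h, 5% at 168 h and 50% at 720 h. Such a sample is not comparable with one taken on treatment, whichever half-life applies.

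**Step 4: effect of the fix.** If samples are compared at the same time since infusion, with dose and interval unchanged, the timing part of the change is 1.0-fold in this model.

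**The case against.** The strongest objection is that the largest swings and material accumulation do not occur together. The 19 h belongs to the drug, from a phase I study of 14 patients. If PEG cleared that fast at a constant rate, steady-state build-up over a first dose, 1/(1 − 2^(−τ/T)), would be 1/(1 − 1/21.4) = 1.05-fold twice weekly and 1/(1 − 1/459) = 1.00-fold weekly, so there would be almost nothing to hide. If PEG clears slowly, build-up matters but the swing is small. This stands as a limit on size and rules out presenting 21- to 459-fold as the expected effect. It does not remove the point. A false rise needs no real build-up, and at 72 h with weekly dosing the swing is 5.0-fold against a build-up of 1/(1 − 1/5.04) = 1.25-fold.

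A reader might infer that even complete testing would be uninterpretable. The protocol does not support that. Nothing in it says that timing shifts between entry and later visits, and timing unrelated to calendar time adds noise to individual changes without moving the cohort summary systematically.

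A reader might also infer that the infusion time is certainly lost. Section 9.3 refers to a stand-alone variable list and a paper case report form, neither of which is shown, and either may hold it.

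Two further inferences go too far. Allowing more than one laboratory does not show that assays differ. Asking for blood to be drawn before an infusion would sit uneasily with the non-interventional design in 9.3 and 10.1. Finally, Table 2 already captures regimen and dose changes, so that part needs no new field.

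**Conclusion.** The concern holds in a limited form. On the variables listed in the protocol, an individual change in plasma PEG cannot be separated from time since the last infusion, and footnote 6 allows post-treatment levels into the same row. The effect could be very large (21- to 459-fold between peak and next dose) only if plasma PEG followed the drug's half-life. It is 2.2- to 5.0-fold at an assumed 72 h, 1.4- to 2.0-fold at an assumed 7 days, and 1.1- to 1.2-fold at an assumed 30 days, where it would hardly matter. The documents do not say which case applies, and these ratios are extremes, not typical pairs of visits.

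The figures rest on mono-exponential decline, a constant dose and interval, and twice weekly taken as every 84 h. The endpoint is secondary and the study is descriptive, so no error rate or sample size is affected. The correction is worth making because it is cheap and has to be in place when samples are taken. It becomes a one-line clarification if the stand-alone variable list already has the fields.

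**What to change.** - In 9.3.2 and Table 2, add for every PEG sample the date and time of sampling and the date, time and dose of the last infusion. If the stand-alone variable list already holds these items, say so in 9.3.2.
- Record which laboratory and assay produced each result.
- State what footnote 6 means for the PEG row.
- In 9.7.4, present PEG change by time since last infusion and by regimen, and show samples taken after stopping treatment separately.

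The cost is a few extra eCRF fields, slightly more work for sites, and fewer pairs that count as comparable in the main PEG summary. It needs no extra visit or blood draw and does not change when blood is drawn.
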